Official Title: Develop the Mini-flipped Game-based Learning Strategies in Modified Mediterranean Diet Interventions for Eating Behavior and Cognitive Performance Among Older Adults in the Community

NCT number: NCT04788446

Document date: July 6th, 2021

Study Protocol

Background

The world is facing an aging population and the number of people with mild cognitive impairment and dementia is increasing, causing a huge burden of medical costs for individuals, families and society. Previous studies have shown that the Mediterranean Diet (MD) can prevent cognitive decline, but older adults are less likely to follow the Mediterranean Diet and have little knowledge about the risk of dementia and protective factors of the diet. The Game-based learning can enhance the learning effectiveness and motivation of the elderly. In this study, the content of the Asian version of the Mediterranean Diet Pyramid and the local food materials from Taiwan will be integrated into the nutritional health education with game strategies of the Modified Mediterranean diet.

Objective

The purpose of this study was to explore the effect of developing Mini-flipped Game-based learning Strategies in Modified Mediterranean diet learning intervention to promote eating behavior and cognitive function of elderly people in community.

Methods

1. Study design:

This study was designed as a cluster randomized controlled trial. First, six communities were selected from Taipei Beitou District, and then randomly assigned to the experimental group and the control group by computer. A total of 80 elderly people were included in this study. The inclusion conditions of the research subjects include: (1) the elderly over 65 years old; (2) Those who have no visual or hearing impairment or mental impairment and can communicate in Chinese and Taiwanese; (3) Those who are willing to participate in the research and fill in the voluntary consent form. Exclusion criteria were :(1) diagnosed with cognitive dysfunction, brain injury and loss

of consciousness for more than 30 minutes or other central nervous system diseases; (2) Suffering from serious diseases, such as organ failure of heart, liver and lung, end-stage kidney disease, general paralysis, end-stage cancer or chemotherapy, and diagnosis of mental diseases.

2. Research tools:

The measurements included a demographic information, the Mediterranean Diet score, the Chinese version of the Montreal Cognitive Assessment Scale, the Chinese version of the Cognitive Failures Questionnaire, the Nutrition Knowledge for the Elderly Scale, the Chinese version Pittsburgh Sleep Quality Index, and the Center for Epidemiological Studies Depression Scale. The study was a single-blind design and was measured at the pre-test (week 0) and post-test (week 8).

3. Intervention approaches:

The experimental group used a Mini-flipped game-based learning strategies in modified Mediterranean diet learning intervention, and the duration of the intervention was 8 weeks, with 40-minute Mini-flipped game-based learning strategies in modified Mediterranean diet learning each week, which the content included: the relationship between the Mediterranean diet and dementia, knowledge of the Mediterranean diet, and how to incorporate local ingredients into the Mediterranean diet. The control group was given a leaflet on balanced diet and nutrition in elderly by the Health Promotion Administration.

Statistical Analysis Plan

SPSS25 software was used for data analysis. The scores of socio demography, eating behavior, cognitive function, nutritional knowledge, depression and sleep in the two groups were described by the descriptive statistical methods, such as percentage, mean and standard difference. Chi-square test (χ^2 test), Fisher's exact test or independent t-test were used to test the homogeneity of the two groups of data. In this study, generalized estimating equations (GEE) were used to measure the differences in dietary behavior, cognitive function and nutritional knowledge between the two groups before and after intervention. Two-tail test was used for all statistical analyses, and the significance level $\alpha=0.05$ was set.

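### The allocation rule for six communities states no split and no balancing, and the SAP's GEE names no baseline covariates, so sizeable chance differences between arms are left unaddressed

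*Combined protocol and SAP*

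**What the plan says.** Under Methods, 1. Study design, the protocol says "This study was designed as a cluster randomized controlled trial". On allocation it says only this: "First, six communities were selected from Taipei Beitou District, and then randomly assigned to the experimental group and the control group by computer". The size is given in one line: "A total of 80 elderly people were included in this study". There is no allocation ratio, number of communities per arm, blocking, stratification, matching, balancing factor or community size.

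The Statistical Analysis Plan deals with baseline comparability by testing: "Chi-square test (χ^2 test), Fisher's exact test or independent t-test were used to test the homogeneity of the two groups of data". For the outcomes, "generalized estimating equations (GEE) were used to measure the differences in dietary behavior, cognitive function and nutritional knowledge between the two groups before and after" the intervention. No covariates are named for that model.

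**The concern.** The draw of six units is the trial's main protection against confounding by community. Communities within one district can differ in age, education, usual diet and access to activities. With about three per arm, such differences do not average out. A factor that affects how people respond to an eight-week learning programme can fall mostly in one arm and be read as an effect of the programme.

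The homogeneity tests do not protect against this. They describe an imbalance once it has happened, and the SAP gives no step that follows from a positive result. Neither the design nor the analysis therefore states any means of limiting or absorbing chance imbalance.

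If the number of communities per arm is also left to chance, precision suffers. In a 1:5 split, the effect in the smaller arm cannot be told apart from the character of a single community.

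**Working it through.** **Inputs from the documents.** Six communities, two groups, 80 participants. The 80 cannot be reproduced, because no effect size, SD, power, ICC or dropout rate is given.

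**Assumptions.** Equal community sizes, m = 80/6 = 13.3. ICC from 0.01 to 0.10. Person-level SD = 1. Normally distributed community means.

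**Step 1: number of communities per arm, if each were assigned independently.** P(k in one arm) = C(6,k)/64.

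| Split | Probability | Efficiency against 3:3, 4ab/36 |
|---|---|---|
| 3:3 | 20/64 = 31.3% | 1 |
| 2:4 | 30/64 = 46.9% | 0.89 |
| 1:5 | 12/64 = 18.8% | 0.56 |
| 0:6 | 2/64 = 3.1% | 0 |

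Unequal arms: 44/64 = 68.75%.

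**Step 2: chance baseline difference under a 3:3 draw.** The variance of a community mean is ICC + (1 − ICC)/m. The SD of the arm difference is the square root of that variance times √(1/3 + 1/3) = 0.816.

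| ICC | SD of a community mean | SD of arm difference | P(difference > 0.25 SD) |
|---|---|---|---|
| 0.01 | 0.290 | 0.237 | 29% |
| 0.05 | 0.348 | 0.284 | 38% |
| 0.10 | 0.409 | 0.334 | 45% |

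At ICC 0.05, P(difference > 0.5 SD) is 8%.

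**Step 3: what plain 3:3 achieves.** Over independent assignment with both arms filled, the root-mean-square SD of the arm difference is 0.900 community-level SDs. Under 3:3 it is 0.816, about 9% lower. At ICC 0.05 the chance of exceeding 0.25 SD goes from 41.8% to 37.9%. Equal numbers alone therefore do little for balance; the small number of communities is the problem.

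**Step 4: what a balance-constrained 3:3 draw achieves.** Sets of six community means were simulated on two independent scored variables and one unrelated variable. The 20 splits were ranked by the sum of squared arm differences on the scored variables. Results at ICC 0.05:

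| Draw from | Scored variable, > 0.25 SD | Scored variable, > 0.5 SD | Unrelated variable, > 0.25 SD |
|---|---|---|---|
| All 20 | 38% | 8% | 38% |
| Best 14 | about 25% (25% to 26% between runs) | about 1.4% (1.3% to 1.4%) | 38% |
| Best 10 | 16% | 0.2% | 38% |

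For the best 14, the chance of exceeding 0.25 SD on a scored variable is 17% at ICC 0.01 and 34% at ICC 0.10.

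**Step 5: forced pairs.** The 20 splits are 10 ways of dividing the communities, each counted twice by exchanging the arms. Any two communities are together in 4 of the 10 and apart in 6. Keeping the best 14 drops 3 of the 10, so every pair keeps at least 4 − 3 = 1 division together and 6 − 3 = 3 apart. No pair can be forced. Keeping the best 10 drops 5, which can remove all 4 divisions in which a pair is together. In simulation this left at least one pair always apart in about 56% of draws.

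**Step 6: price in permissible allocations.** The smallest two-sided randomisation-test p is 2/20 = 0.10 for all 3:3 splits and 2/14 = 0.14 for the best 14.

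**The case against.** **The text does not describe unrestricted randomisation.** A reader might infer from the allocation sentence that each community was assigned independently and that unequal arms were therefore likely. The documents do not support that. A computer draw of three from six fits the sentence equally well. The 69% figure is conditional, and the firm finding is that neither the split nor any restriction is stated.

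**A reader might also infer that a 3:3 rule would largely cure baseline imbalance at no cost.** It would not. Step 3 shows a reduction of about 9% in the SD of the arm difference. Better balance needs constraint on named variables, which has a price.

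**The analysis already removes part of the problem.** Outcomes are measured at week 0 and week 8, and the GEE compares the groups before and after. Read as a group-by-time model, it cancels a constant baseline difference in the outcome itself. This stands, and the percentages above are raw baseline differences, not biases in the estimated effect. What remains is imbalance in factors that influence change over the eight weeks, such as age or education, which the documents give no means to quantify.

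**The gain from constraint is narrow.** This also stands. A variable unrelated to the two scored ones stays at 38%.

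**The allocation may already be done.** The protocol is written in the past tense. If so, only reporting and the analysis can still change.

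**Conclusion.** The concern holds as a gap in both design and analysis: no split, no balancing on community characteristics and no baseline covariates are stated. The 29% to 45% chance of an arm difference above 0.25 SD applies even if a 3:3 draw was intended. It rests on assumed ICCs and equal community sizes; an ICC above 0.10 would raise it.

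A feasible alternative improves on what is stated. At ICC 0.05 it takes about a third off the chance of a difference above 0.25 SD on the scored variables, and most of the chance of one above 0.5 SD. It does nothing for unrelated factors. The point merits a change to the plan, but it does not show that the arms are in fact unequal or that the result is biased.

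**What to change.** **If allocation is still to come**, replace the allocation sentence with text to this effect:

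> Three of the six communities will be allocated to each group. The 20 possible allocations will be scored for balance on two community-level variables fixed in advance and available before the draw (for example, mean age and mean education of eligible members). The 14 best-balanced allocations will be kept, after checking that no two communities are always together or always apart, and one will be drawn by computer.

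Then name those variables as covariates in the GEE. Two details matter:

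- Enter participants' own values. Two community-level means would leave only 6 − 2 − 2 = 2 degrees of freedom between communities.
- Enter them so that they can act on the contrast of interest, either with a covariate-by-time term or by modelling the week-8 score with the baseline score as a covariate. With complete data, a linear group-by-time GEE gives the same interaction estimate whether or not a time-constant covariate is added as a main effect only.

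**If allocation is done**, report the method, any restriction and the number of communities per arm, and add age, education and the baseline outcome to the GEE in the same way.

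**Cost.** A short script and a few sentences; no extra participants or visits. Community summaries are needed before the draw. Using pre-test scores as balancing variables would require recruitment and week-0 testing before allocation, a sequence the documents do not describe. Permissible allocations fall from 20 to 14, so the smallest two-sided randomisation-test p rises from 0.10 to about 0.14. The SAP plans no such test, so this matters only if one is added.

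### Does comparing game-based Mediterranean-diet sessions with a balanced-diet leaflet leave the trial unable to meet its objective?

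*Combined protocol and SAP*

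**What the plan says.** The Objective section states that the aim is to "explore the effect of developing Mini-flipped Game-based learning Strategies in Modified Mediterranean diet learning intervention to promote eating behavior and cognitive function" in older community residents. Methods, 1. Study design describes six communities "randomly assigned to the experimental group and the control group by computer", with 80 participants in total. There are two arms and no third.

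Methods, 3. Intervention approaches defines the experimental arm: "the duration of the intervention was 8 weeks", "with 40-minute Mini-flipped game-based learning strategies in modified Mediterranean diet learning each week". The topics are "the relationship between the Mediterranean diet and dementia, knowledge of the Mediterranean diet, and how to incorporate local ingredients into the Mediterranean diet". For the comparator it says only: "The control group was given a leaflet on balanced diet and nutrition in elderly by the Health Promotion Administration". No sessions and no Mediterranean-diet material are described for that arm.

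Methods, 2. Research tools lists "the Mediterranean Diet score" among the measures. The Statistical Analysis Plan compares the two groups before and after the intervention with generalized estimating equations (GEE) on dietary behaviour, cognitive function and nutritional knowledge. It names no contrast aimed at the teaching format alone.

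**The concern.** The objective opens with "The purpose of this study was to explore the effect of developing Mini-flipped Game-based learning Strategies", the official title also leads with the game-based strategies, and the Background gives game-based learning a rationale of its own. A reader could take the teaching method to be the thing under test. On that reading the comparator is wrong, because the control arm lacks the game format and, as described, also lacks the Mediterranean-diet teaching and the weekly sessions.

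The diet outcome sharpens the worry. It scores adherence to a diet that, as described, is taught only in the experimental arm. A class of the same length on the same topics, without games, might also improve that score relative to a balanced-diet leaflet; the documents give no figure on this, so it is an assumption. Weekly sessions might also affect cognitive, sleep or depression scores through contact and attention. At stake is whether a positive result could be credited to game-based learning when content or contact had produced it.

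**Working it through.** The documents give no total contact time, effect size or power calculation, so there is no figure of the plan's own to reproduce. The check has three parts.

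**1. How the arms differ** (Methods, 3. Intervention approaches)

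| Feature | Experimental | Control |
|---|---|---|
| Teaching method | mini-flipped, game-based | leaflet |
| Diet content | modified Mediterranean diet | balanced diet |
| Scheduled session time | 8 weeks × 40 minutes = 320 minutes | none described |

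Three limits apply. Zero control minutes is inferred from a leaflet-only description. The text does not say that the sessions were held in groups. The leaflet is not reproduced, so its overlap with Mediterranean-diet advice cannot be checked.

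**2. What the contrast estimates**

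Let g, c and t be the effects of game format, diet content and session time, and let i collect any interactions among them. Every experimental participant has all three features, and every control participant has none as described. The between-arm difference in change therefore estimates

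Δ = g + c + t + i.

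The indicators for the three features are each identical to the arm indicator. The data determine the sum Δ and nothing finer, and covariate adjustment or a different GEE specification cannot alter that. The share g/Δ is not even confined to the range 0 to 100%, since components may have opposite signs or interact. It is simply not identifiable. None of this biases Δ as the effect of the whole programme against a leaflet.

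**3. What the plan claims to estimate**

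- *Objective:* the full sentence does not stop at the game strategies. It sets them within a Mediterranean-diet learning intervention aimed at eating behaviour and cognition.
- *Official title:* same construction, with the strategies placed in the diet interventions.
- *Background:* the diet pyramid and local foods are to be built into nutrition education that uses game strategies. That is one combined product.
- *Methods, section 3:* the experimental arm carries the same compound name, and its content is listed as Mediterranean-diet teaching.
- *Statistical Analysis Plan:* one experimental-versus-control comparison. No hypothesis or test concerns the format separately from content or contact.

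Taken together, the quantity described is Δ, and Δ is what the analysis delivers. If the Objective were rewritten to say so outright, the arms, outcomes, 80 participants, GEE model and two-sided 0.05 level would all stay as they are, and every estimate and p-value would be the same.

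**The case for a change.** The strongest case for acting is that the ambiguity is real and cheap to remove. The title and Background present the learning method as the novelty, and the protocol nowhere says that the comparison is of a whole programme or that no claim about the format will follow. One sentence would settle it, at no cost in participants or data, and would still be useful when results are reported.

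Part of this stands. The aliasing is complete, the wording admits both readings, and a careful report should describe the comparison as an 8-week session-based Mediterranean-diet programme against a balanced-diet leaflet. A conclusion that credited the game format alone would not be supported.

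The rest does not make a defect in the plan. The feared misstatement is a forecast about a later publication; the documents contain no such conclusion. Both arms are openly described, so any reader can see what was compared.

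Isolating the format would need a comparator with the same diet content and session time but no games, which is a different question. Adding that as a third arm would leave 6 / 3 = 2 communities per arm, against 6 / 2 = 3 now, assuming an even split, which the documents do not state. Testing a multicomponent education programme against a public-health leaflet is an ordinary pragmatic choice.

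**Conclusion.** No change follows. The arms do differ at once in teaching method, diet content and scheduled session time (320 minutes against none described), so the contribution of the game-based format cannot be identified. But the plan does not undertake to identify it. Read whole, the objective describes an integrated programme, and on this point the planned between-group comparison is a legitimate estimate of that programme's effect against a leaflet. Rewording would change no design feature, analysis or result.

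This rests on two assumptions: that the objective is read as the package, which its full sentence, the title and the Background all support, and that the control arm received the leaflet and no sessions, as the description implies. If the investigators did mean to test the format by itself, these two arms could not do so and no analysis would rescue it. The ordinary caution when reporting is to credit any effect to the programme as a whole.

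### Individual-level homogeneity tests do not fit the randomisation of six communities if outcomes cluster, and a non-significant result cannot show comparability at any degree of clustering (minor)

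*Combined protocol and SAP*

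**What the plan says.** Methods, 1. Study design: "This study was designed as a cluster randomized controlled trial". The unit of allocation is the community: "six communities were selected from Taipei Beitou District, and then randomly assigned to the experimental group and the control group by computer". On size: "A total of 80 elderly people were included in this study". The documents do not state the split of communities or people between arms, the community sizes or an ICC.

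Statistical Analysis Plan: demographics, outcomes, "nutritional knowledge, depression and sleep in the two groups were described by the descriptive statistical methods". After chi-square, the next tests are named: "Fisher's exact test or independent t-test were used to test the homogeneity of the two groups of data". All tests are two-sided at 0.05. No cluster adjustment or community-level comparison is mentioned for these tests. Generalized estimating equations (GEE) appear only for the outcome comparison, "used to measure the differences in dietary behavior, cognitive function and nutritional knowledge between the two groups before and after intervention", so they do not cover the homogeneity tests.

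The SAP does not say when homogeneity is tested. Baseline is the natural reading, because the before-and-after comparison is given to the GEE.

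**The concern.** There are two separate difficulties.

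First, a significance test of baseline balance asks whether the gap between arms is larger than the allocation would produce by chance. Here chance acted on six communities, not on 80 people. If people in the same community resemble one another, the arms will differ by more than an individual-level test expects, and its p-value will be too small.

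Second, and whatever the ICC, failing to reject is not evidence that the arms are alike. With about 40 people per arm, quite large gaps pass unnoticed.

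At stake is what a reader is told about the baseline table. A significant result could be taken as a sign of faulty allocation or recruitment when it reflects ordinary clustering. A non-significant one could be reported as comparability that was never shown.

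**Working it through.** **Inputs from the documents.** 6 communities, 2 arms, 80 people, two-sided alpha 0.05. Mean community size is 80/6 = 13.3.

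**Assumed, because the documents do not say.** Three communities and 40 people per arm; ICC from 0 to 0.10. Other splits are checked below.

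**1. The plan's own error rate.** No inputs are given from which to rebuild the sample size of 80, so the only figure to check is the 5% level. Simulating the t-test at ICC 0 (communities of 14, 13 and 13 per arm, 200,000 runs) gives 5.0%. The stated level holds there.

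**2. The level when ICC > 0.** Design effect DE = 1 + (13.3 − 1) × ICC. Approximate rejection rate under sound allocation = 2 × [1 − Φ(1.96/√DE)].

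| ICC | DE | 1.96/√DE | Formula | Simulation |
|---|---|---|---|---|
| 0.01 | 1.123 | 1.849 | 6.4% | 6.5% |
| 0.05 | 1.617 | 1.541 | 12.3% | 12.3% |
| 0.10 | 2.233 | 1.312 | 19.0% | 19.4% |

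A 2:4 split of communities gives 12.4% and 19.5% at ICC 0.05 and 0.10. Uneven communities (22/10/8 against 20/12/8) give 13.8% and 21.9%. The finding therefore does not depend on the unstated split, but it does depend on the ICC.

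**3. Categorical variables.** At an assumed 30% prevalence and ICC 0.05, chi-square rejects 12.4% (ICC defined on the binary scale) or 9.1% (on a latent normal scale). Fisher's test is conservative: 3.8% or 3.4% at ICC 0.01, and 8.6% or 6.0% at 0.05. It passes 5% only from an ICC of roughly 0.03 to 0.05.

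**4. Smallest gap that reaches p < 0.05.** For the t-test with 78 df this is 1.991 × √(2/40) = 0.445 observed SD. The calculation contains no ICC, so it applies at any ICC. For chi-square, 12/40 against 20/40 gives p = 0.068 and 12/40 against 21/40 gives p = 0.041, so a 20-point gap passes and a 22.5-point gap is flagged.

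**5. Power at ICC 0.** For a true difference of 0.3 SD the noncentrality is 0.3 × √(40/2) = 1.34, giving power of 26.3%. Reaching 80% power needs about 0.63 SD.

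**6. Would a community-level test repair this?** Observed gaps of at least 0.3 SD arise in 18%, 29% and 37% of allocations at ICC 0, 0.05 and 0.10. The share missed is:

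| ICC | Individual t-test | t-test on six community means |
|---|---|---|
| 0 | 72.1% | 78.0% |
| 0.05 | 57.4% | 84.5% |
| 0.10 | 47.2% | 87.2% |

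A permutation test is no better. A 3:3 split has 20 possible allocations, so the smallest two-sided p is 2/20 = 0.10. The community-level test has the right level but misses more.

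**7. Adjusting for the week-0 score.** With correlation ρ between the two visits and equal variances, the SD of an effect estimate is proportional to √[2(1 − ρ)] for a before-after contrast and √(1 − ρ²) after adjustment. The ratio is √[(1 + ρ)/2]: 0.866 at ρ = 0.5 and 0.922 at ρ = 0.7, or reductions of 13% and 8%. Simulation over the same assumed correlations gave about 6 to 14%.

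**The case against.** The strongest reply is that nothing hangs on these tests. The SAP does not choose covariates from them, does not alter the GEE because of them, and does not say that a non-significant result will be read as comparability. It already describes the variables by group. All of that stands, and it is why the point is minor.

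A second reply is that the SAP speaks of homogeneity of the data and not of the allocation. If the question is only whether the people in these particular communities have equal arm means, with community effects held fixed, the t-test is not inflated: simulation gave 4.5% at ICC 0.05 and 4.3% at 0.10. This also stands. The inflation is relative to the random allocation of communities, which is the usual reference in a cluster trial but is not spelled out in the plan. The second difficulty is untouched, since low power does not depend on which null is meant.

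A third reply is that this repeats the question of how the GEE handles communities. The root is shared, but the sentence and the remedy differ: correcting the GEE would leave the homogeneity tests as they are.

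A reader might also infer that an imbalance passed as homogeneous would bias the treatment effect. The documents do not support that. They give no prognostic strength for any baseline variable, the tests do not feed the GEE, and any figure for a shift would rest on assumed coefficients and on a model form that the SAP does not name.

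**Conclusion.** The concern holds, at minor severity. If ICC > 0, the t-test and chi-square p-values are too small relative to the community allocation: about 6%, 12% and 19% rejection at assumed ICCs of 0.01, 0.05 and 0.10. At ICC 0 the t-test holds its level, and Fisher's test stays below 5% at very small ICCs. Since no ICC is given, the inflation is a range and not a finding about this trial's data.

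The part about non-significance needs no ICC. It rests on roughly 40 people per arm.

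The consequence is a possibly misleading statement about comparability. No shift in the planned GEE estimate has been shown, and nothing in the documents indicates that the arms in fact differed. How the GEE accounts for communities is a separate issue, not settled here.

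**What to change.** Delete the homogeneity tests from the Statistical Analysis Plan and do not put a community-level test in their place. Report baseline by arm and by community, with means or percentages and standardised differences between arms. This costs a wording change and one re-laid-out table, with no new data. The community columns will be coarse: with 13.3 people on average, one person moves a percentage by 1/13.3, about 7.5 points.

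Separately, and whatever imbalance is seen, state that each week-8 outcome is analysed with its own week-0 score as a covariate. Both scores are already collected, and precision improves over a before-after contrast. This changes the specification of the outcome analysis, so it is more than an edit to the baseline table, and it uses only people measured at both visits.

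If the analysis is already complete, re-report the table in this form and label the adjustment post hoc.

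### Six communities are randomised, but the planned GEE names neither community nor a correction for six clusters, so its 5% level is not protected

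*Combined protocol and SAP*

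**What the plan says.** Under Methods, 1. Study design, the protocol states that "This study was designed as a cluster randomized controlled trial" and that "six communities were selected from Taipei Beitou District, and then randomly assigned to the experimental group and the control group by computer". It adds that "A total of 80 elderly people were included in this study". It does not say how many communities went to each arm or how many people came from each.

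The Statistical Analysis Plan has one between-group analysis of outcomes: "generalized estimating equations (GEE) were used to measure the differences in dietary behavior, cognitive function and nutritional knowledge". The contrast is described as one "between the two groups before and after intervention". It also says "Two-tail test was used for all statistical analyses", with α = 0.05. Outcomes are measured at week 0 and week 8 (Methods, 2. Research tools). The plan does not give the GEE subject variable, working correlation, covariance estimator, reference distribution, small-sample correction or ICC. Community is not mentioned in the Statistical Analysis Plan.

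The chi-square, Fisher and t-tests are named for checking group homogeneity, and depression and sleep appear only under description. This point therefore concerns the three GEE domains alone.

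**The concern.** GEE allows only for correlation within whatever it is told is a subject. Two readings of the plan are natural.

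- **(a) The subject is the person, measured twice.** The before-and-after wording fits this best. Stable differences between communities cancel from the group-by-time contrast. Differences between communities in their change do not cancel, and they are ignored.
- **(b) The subject is the community.** The sandwich variance then rests on six clusters. Without a correction, and with a normal or chi-square reference, it is too small whatever the ICC.

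The GEE carries both aims in the Objective (eating behaviour and cognitive function) as well as nutrition knowledge. If its p-values are too small and its intervals too narrow, a significant result could be ordinary variation between six communities. Readers could not correct for this themselves, because the plan does not commit to reporting community sizes or the ICC.

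**Working it through.** **Inputs from the documents:** 6 communities, 80 people, two-sided α = 0.05, two time points. Mean community size m = 80/6 = 13.33.

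**Assumptions (not in the documents):** ICC of the pre-post change from 0 to 0.10, the same in both arms; a 3 v 3 split, with 2 v 4 as a sensitivity case; all 80 people analysed. The simulations also assume a within-person pre-post correlation of 0.6 and a stable community ICC of 0.05, with 40,000 null replicates per setting unless noted.

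**The plan's own figure.** α is a setting, and 80 has no stated derivation, so there is no calculation to reproduce. A critical value of 1.96 returns 2 × (1 − Φ(1.96)) = 5.0%, but only if the 80 people are independent.

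**Reading (a), person as subject.** Design effect DE = 1 + (13.33 − 1) × ICC. Actual type I error = 2 × (1 − Φ(1.96/√DE)).

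| ICC of change | DE | Formula | Simulated, robust SE, sizes 14/13/13 per arm |
|---|---|---|---|
| 0 | 1.00 | 5.0% | 5.5% |
| 0.01 | 1.12 | 6.4% | 7.1% |
| 0.02 | 1.25 | 7.9% | 8.8% |
| 0.05 | 1.62 | 12.3% | 13.8% |
| 0.10 | 2.23 | 19.0% | 20.8% |

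About 0.5 points of each simulated figure is not due to clustering, as the row at ICC 0 shows. A separate simulation of change scores agreed to within about 0.6 points.

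**Reading (b), community as subject, uncorrected sandwich, normal reference.** With three equal clusters per arm, the sandwich divides each arm's sum of squares by 3² = 9, where the unbiased variance of the mean divides by 3 × 2 = 6. The variance is therefore 6/9 = 2/3 of what it should be. The test rejects when |t| on 4 df exceeds 1.96 × √(2/3) = 1.60, which has probability 18.5%. The ICC does not enter. Simulated:

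- 3 v 3, near-equal sizes: 18.5–18.8% over ICC 0 to 0.10
- 3 v 3, sizes 8/12/20 per arm: 20–22%
- 2 v 4: about 23% with about 13 people per community; 20–22% with 20/20 v 10/10/10/10

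**Alternatives, simulated type I error over ICC 0 to 0.10 (2 v 4 with about 13 per community):**

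| Method | 3 v 3, near-equal | 3 v 3, 8/12/20 | 2 v 4 |
|---|---|---|---|
| Two-stage community t-test, 4 df | 5.0–5.2% | 4.7–5.1% | 4.9–5.0% |
| GEE by community, Kauermann-Carroll, t on 4 df | 4.9–5.1% | 5.3–6.1% | 7.0–7.4% |
| GEE by community, Mancl-DeRouen, t on 4 df | 2.6–2.9% | 2.6–3.1% | 4.0–4.3% |

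A REML mixed model with a random community effect (4,000 replicates, 3 v 3 only) gave 4.9–10.7% with a normal reference and 0.6–3.8% with t on 4 df. Kenward-Roger and Satterthwaite degrees of freedom were not simulated.

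A permutation test cannot reach 0.05. A 3 v 3 split has C(6,3) = 20 allocations, so the smallest two-sided p is 2/20 = 0.10; for 2 v 4 it is 1/15 = 0.067.

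**The case against.** **The plan is silent; that does not show how the GEE was run.** A corrected community-level GEE may have been used and not recorded. This is fair as a statement about practice. The point here is about the written plan, which does not protect the level under either natural reading. The claim under (b) is limited to the uncorrected sandwich with a normal or chi-square reference.

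**The size under (a) rests on an assumed ICC, equal in both arms.** This stands as a limit. At ICC 0.01 the inflation is small. One arm has weekly sessions and the other a leaflet, so the extra variation in change might sit mainly in the taught arm. With ICC there only (3 v 3), type I error is 9.5% at 0.05 and 13.5% at 0.10, which is lower but still well above 5%.

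**The two-stage test does not hold 5% everywhere.** This stands in part. With 2 v 4 and the extra variance only in a two-community taught arm, it rises to about 7% at ICC 0.05 and 8.6% at 0.10. Corrected GEE is worse there (9–10%). With 2 v 4 at 40 people per arm and equal ICCs, a t-test on community means is conservative (about 3.5–4.5%). At 3 v 3 the two-stage test stays at 5.0–5.5% even with unequal arm variances.

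**Corrected GEE would also do.** For 3 v 3 with near-equal sizes, Kauermann-Carroll with t on 4 df is adequate and keeps the planned method. It is less robust once sizes or the split are uneven, and neither is stated.

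**Conclusion.** The concern holds. Followed as written, the analysis does not control type I error at 5% for diet, cognition or nutrition knowledge. Under (b) with an uncorrected sandwich, the error is about 18.5% at 3 v 3 and 20–23% with uneven sizes or a 2 v 4 split, and this needs no assumption about the ICC. Under (a) it runs from 6.4% to 19.0% by formula over ICC 0.01 to 0.10, and is essentially nominal only if communities do not differ in their change. The ICC, split, community sizes and complete data are assumed. They affect how large the inflation is, but the plan fixes none of them in a way that would remove it. This must be fixed before the between-group results are relied on.

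**What to change.** For the Mediterranean Diet score, the two cognitive scales and the nutrition knowledge scale, replace the GEE with a two-stage community-level analysis:

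1. Regress post-test on pre-test, without group.
2. Average the residuals within each community.
3. Compare the six community means with a t-test on 4 df (critical value 2.776).

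State the split and the number of people per community, and report the ICC of the change. If the split is 3 v 3 with near-equal sizes, GEE with community as subject, the Kauermann-Carroll correction and t on 4 df is an acceptable fallback. Do not rely on a permutation test.

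**Cost.** SAP wording and a re-run; no new participants. The plan's past tense suggests that the data are already in hand. If they have been analysed, the changed analysis should be labelled post hoc.

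The real price is precision. The interval width ratio to the person-level analysis is (2.776/1.96) × √DE = 1.50, 1.80 and 2.12 at ICC 0.01, 0.05 and 0.10.

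For 80% power on 4 df the noncentrality is 3.761, and SE = √((2/3) × (ICC + (1 − ICC)/13.33)). The detectable difference is therefore 0.84 SD at ICC 0, 0.89 at 0.01 and 1.26 at 0.10. For 80 independent people it would be 2.80 × √(4/80) = 0.63 SD. These are SDs of the change score, without baseline adjustment. At the assumed pre-post correlation of 0.6, multiplying by √(2 × 0.4) = 0.894 turns 0.89–1.26 into about 0.80–1.12 SD of the outcome.

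The SAP should therefore say that a non-significant result will be read as imprecise, not as evidence of no effect.
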